Minervini et al. analyzed the pseudocapsule integrity of 304 specimens after TE, founding that 51% of the specimens had an intact pseudocapsule and 49% had infiltrating tumor cells on the pseudocapsule. but all specimens had negative cut margins and there is no statistical difference in 5-year progression-free survival. thus they concluded that enucleation for renal cancer is a safe surgical procedure. In the past 10 years, our team has performed more than 500 kidney cancer enucleations without any positive margins and no patient has experienced in local recurrence. In addition, traditional PN requires temporary blockage of the renal artery to achieve a relatively bloodless operating environment to ensure the safety of tumor removal. But prolonged warm ischemia is bound to affect the function of normal kidney tissue. Therefore reducing thermal ischemia time up to zero ischemia time has become a quest for surgeons. The combination of zero-ischemia technique on the basis of kidney cancer enucleation is a field that has rarely been touched.

Therefore reducing thermal ischemia time up to zero ischemia time has become a quest for surgeons. Clinically, the combination of zero-ischemia technique on the basis of kidney cancer enucleation is a field that has rarely been touched. In the last 3 years, our team has performed nearly 100 cases of zero-ischemic renal tumor enucleation, and this procedure can maximize the protection of renal parenchyma and renal function under the premise of ensuring tumor safety. In conclusion, if zero ischemia enucleation can be applied and popularized to limited renal cancer surgery, it will benefit a large number of patients and improve the prognosis.

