## **3. Study content and design**

This study aims to evaluate the effectiveness and safety of the surgery by using renal cancer patients who met the inclusion criteria. Summarizing the preoperative, perioperative, and postoperative data, and evaluating the operative time, intraoperative bleeding, postoperative hospitalization days, postoperative complication rate, postoperative short-term, intermediate, and long-term renal function indexes, overall survival, tumor-free survival, progression-free survival and postoperative renal cancer recurrence rate of the patients.

Statistical software is used to describe the characteristics of patient data. T-test, rank sum test, multi-factor regression, and cox regression are used to investigate the effects of each factor on the treatment outcome and prognosis of patients undergoing zero-ischemic renal enucleation, to describe whether there are differences in the safety and efficacy of zero ischemic renal enucleation compared with traditional

partial nephrectomy for the treatment of stage T1 renal carcinoma.

This study used a retrospective research trial design to include 73 patients who underwent zero-ischemic enucleation and 73 patients who underwent traditional partial nephrectomy from 2014 to 2022, for a total of 146 patients. The formula for calculating the sample size is as follows.

$$n = [z_{\alpha}\sqrt{2\bar{p}\bar{q}} + z_{\beta}\sqrt{p_0q_0 + p_1q_1}]^2 p / (p_1 - p_0)^2$$

Figure 1. Estimated sample size calculation

note:  $Z_{\alpha}$ 、 $Z_{\beta}$  are the quartiles under standard normal distribution.

$p_1$ : Expected morbidity in the exposed group.

$p_0$ : Expected incidence in the control group.

$q_1$ :  $q_1 = 1 - p_1$ .

$q_0$ :  $q_0 = 1 - p_0$ .

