## **5. Experimental program**

**5.1** The patients are screened according to the inclusion and exclusion criteria. Then the patients are divided into two groups according to whether they underwent zero-ischemic enucleation or partial nephrectomy, with the zero-ischemic enucleation group as the test group and the partial nephrectomy group as the control group. Describing the preoperative conditions (age, sex, Anatomy of tumor, RENAL score, ABC score, preoperative renal function), the perioperative conditions (operation time, intraoperative bleeding, perioperative complications, negative/positive specimen margins, postoperative renal function changes, postoperative hospitalization days), and the postoperative condition (follow-up renal function, tumor recurrence rate, overall survival, tumor-free survival, progression-free survival).

**5.2** The data of the two groups are corrected for baseline and screened so that there is no statistical difference in the number of patients, gender age, tumor anatomy, renal function and other preoperative conditions between the two groups (t-test/rank sum test  $p > 0.05$ ).

**5.3** The zero ischemic renal enucleation group is grouped according to RENAL score, ABC score and other scoring criteria. Different preoperative tumor score groupings are used as exposure

factors, and the percentage decrease of postoperative renal function compared with preoperative, perioperative complication rate and postoperative survival rate are used as outcome variables to analyze the association between exposure factors and outcome, to investigate the association of different factors on the surgical outcome of zero ischemic renal enucleation.

**5.4** Using zero-ischemic nephrectomy or partial nephrectomy with clamping of the renal hilum as the exposure factor. T-test/rank sum test and one-way regression are used to compare the efficacy indexes such as negative/positive tumor margins, postoperative and follow-up renal function, survival rate, and safety indexes such as perioperative complication rate and intraoperative bleeding between the two groups to investigate whether there is a statistical difference in their treatment safety and efficacy. Then we investigated whether there are statistical differences and correlations between the safety and efficacy of the treatment, and whether there are statistical differences in survival outcomes between the two groups by multifactorial cox regression.

[figure not shown]

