### 6.2 Data description

The measurement data are described as mean standard

deviation ( $\bar{x} \pm s$ ), median, maximum, minimum, and quartiles, and the count data are expressed as percentages (%).

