### **6.3 Statistics**

Data entry: Enter the age, gender, kidney cancer stage and prognosis follow-up of the subjects.

Data management: The data are presented by number, and all personnel except the initial data entry personnel do not have access to the subjects' initial information (including subjects' personal information such as subjects' names, addresses, occupations and other sensitive information). There is no direct contact between the data entry personnel and the subjects, and all privacy of the subjects is protected from disclosure.

All hypothesis tests are two-sided, and differences are considered statistically significant at  $P < 0.05$ . Baseline data are evaluated for comparability between groups, and two-tailed statistical tests are performed at the  $\alpha=5\%$  level. The chi-square test or Fisher's exact probability method is used for comparison between groups for count data, the t-test for comparison between groups for measurement data, and the rank sum test for comparison between groups for nonparametric variables.

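### Section 5.4 assigns t-test/rank sum to positive margins and survival rate, section 6.3 leaves chi-square or Fisher open, and no interval is specified, so the margin conclusion can turn on an unstated choice of test

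*Combined protocol and SAP*

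**What the plan says.** Two sections of the combined protocol and SAP give different tests for the same outcomes.

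- **Section 5.4** (comparison with partial nephrectomy): "T-test/rank sum test and one-way regression are used to compare the efficacy indexes such as negative/positive tumor margins". The same sentence goes on to list renal function, survival rate, perioperative complication rate and bleeding. The type of one-way regression is not stated. The next sentence asks "whether there are statistical differences in survival outcomes between the two groups by multifactorial cox regression".
- **Section 6.3**: "The chi-square test or Fisher" (the sentence continues with Fisher's exact test) "exact probability method is used for comparison between groups for count data". It keeps the t-test for measurement data and the rank sum test for nonparametric variables. It sets two-sided significance at P < 0.05 and does not say when chi-square gives way to Fisher.
- **Section 6.2**: "the count data are expressed as percentages". Neither this section nor any other specifies a confidence interval.
- **Section 3**: 73 enucleation patients and "73 patients who underwent traditional partial nephrectomy from 2014 to 2022", in a retrospective design.
- **Section 1**: "our team has performed more than 500 kidney cancer enucleations without any positive margins and no patient has experienced in local recurrence". No margin rate is given for partial nephrectomy.

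Section 2 lists the comparison between procedures as a secondary objective. Positive margin rate and the survival endpoints are also named in the main objective.

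**The concern.** A margin is positive or negative. Section 5.4 therefore gives a binary outcome to tests that section 6.3 keeps for continuous or ranked data, and section 6.3 offers two tests of its own without a selection rule. When positive margins are few, these tests need not agree at the 5% level. The operations date from 2014 to 2022 and the protocol from February 2023, so the margin results already exist. A test left open can then be settled after the counts are known. Without an interval, a non-significant result also does not show how large a difference remains possible.

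Survival rate in section 5.4 raises a second problem. A t-test or rank sum test on alive/dead status, or on observed times, treats a censored patient as if the outcome were complete. Patients operated on from January 2014 to December 2022 could have had anything from about one month to about nine years of follow-up at the protocol date. If follow-up differs between groups, such a test mixes that difference with the effect of the procedure.

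**Working it through.** **Inputs.** From the documents: n = 73 per group, N = 146 (section 3); two-sided 5% level (section 6.3); no positive margin in more than 500 enucleations (section 1). Assumed: no positive margin among the 73 enucleation patients, and a partial nephrectomy rate of 1% to 10%. The plan states no margin p-value, rate or power to reproduce. The 73 per group cannot be reproduced either, because no values are given for p₀, p₁ or power.

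**Step 1: the four tests at 0/73 v b/73.**

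- Uncorrected chi-square: X² = 146b/(146 − b), on 1 df.
- Equal-variance t-test on 0/1 data: t² = X²(N − 2)/(N − X²), on 144 df.
- Rank sum, tie-corrected, no continuity correction: z² = X²(N − 1)/N.
- Fisher, two-sided: 2 × C(73,b)/C(146,b).

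The first three are nearly the same statistic. For b = 4: X² = 584/142 = 4.113; t² = 4.113 × 144/141.887 = 4.174; z² = 4.113 × 145/146 = 4.085. Fisher is 2 × (73·72·71·70)/(146·145·144·143) = 0.120.

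| Enucleation v partial nephrectomy | t-test | rank sum | chi-square | Fisher |
|---|---|---|---|---|
| 0 v 3 | 0.081 | 0.081 | 0.080 | 0.245 |
| 0 v 4 | 0.043 | 0.043 | 0.043 | 0.120 |
| 0 v 5 | 0.023 | 0.023 | 0.023 | 0.058 |
| 0 v 6 | 0.012 | 0.013 | 0.012 | 0.028 |

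With no enucleation positives, the conclusion differs only at 4 and 5. It also differs at 1 v 7 (0.029, 0.030 and 0.029 against Fisher 0.063). The smallest expected counts at 0 v 4 and 0 v 5 are 4/2 = 2.0 and 5/2 = 2.5. A Yates-corrected chi-square sides with Fisher (0.128 and 0.069), so the word chi-square is itself ambiguous.

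**Step 2: how likely is such a table?** P(4) + P(5) from Binomial(73, p), enucleation at zero:

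| Assumed partial nephrectomy rate | 1% | 2% | 3% | 5% | 7% | 10% |
|---|---|---|---|---|---|---|
| Chance of 4 or 5 positives | 0.6% | 5.5% | 15% | 34% | 36% | 19% |

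If the enucleation rate is instead 0.735%, the exact upper limit for 0/500 (1 − 0.025^(1/500)), the chance that rank sum and Fisher disagree is 3%, 9%, 21% and 25% at 2%, 3%, 5% and 7%.

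**Step 3: what an interval would show.** The exact 95% upper limit for 0/73 is 1 − 0.025^(1/73) = 4.9%. Newcombe 95% intervals for partial nephrectomy minus enucleation, in percentage points: 0 v 0, −5.0 to +5.0; 0 v 4, −0.5 to +13.3; 0 v 5, +0.5 to +15.1. At 0 v 0 there is nothing to test and only the interval is informative. At 0 v 5 the interval excludes zero while Fisher gives 0.058, so the plan must say which governs.

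**Step 4: cost of Fisher.** At a common 3% rate (assumed), the nominal 5% test rejects 4.2% of the time by t-test, 4.1% by rank sum and 0.6% by Fisher.

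**Step 5: regressions with an empty group.** If the one-way regression is logistic, 0/73 in one group gives no finite odds ratio. A Cox fit on simulated times with no events in one group did not converge (log hazard ratios of −24 and −102 with very large standard errors). This shows only what happens with an empty group, not that one will occur.

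**The case against.** Section 6.3 is the general statistical section, and a biostatistician following it would probably choose Fisher at expected counts of 2.0 or 2.5. That is fair, but the section does not say so.

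A reader might infer that the result flips according to whether section 5.4 or section 6.3 is followed. The figures do not support this: uncorrected chi-square under 6.3 gives the 5.4 answer. The split is Fisher against the other three tests, and it already lies inside 6.3.

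A reader might also infer that the team's own series implies a table where the tests disagree. It does not. That series covers enucleation only, is not stated to be the source of the 73, and says nothing about partial nephrectomy. If that rate is also near zero, the result is an uninformative test, not a flip.

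On survival, section 5.4 also plans a Cox model, which handles censoring. That stands, but survival rate remains in the t-test/rank sum list, so two methods apply and one is unsuitable. It is tempting to add that the enucleation group has shorter follow-up, since "In the last 3 years, our team has performed nearly 100 cases of zero-ischemic renal tumor enucleation". The text does not confine zero-ischemia cases to those years, and it does not say that recurrence will be a crude proportion.

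Finally, section 6.2 concerns description and does not exclude intervals from the regression models. The supportable statement is that no interval is specified, not that none will be reported.

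**Conclusion.** The point holds in a limited form and should be fixed. Sections 5.4 and 6.3 contradict each other on binary outcomes, section 6.3 has no selection rule, and survival rate is placed under tests that ignore censoring. These follow from the text alone.

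The numerical consequence is conditional. With no enucleation positives, the conclusion depends on the test only at 4 or 5 partial nephrectomy positives (5.5% or 6.8% of 73). Whether that is a remote or a one-in-three possibility depends on a rate the documents do not give.

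The documents do not show that survival events will be few, since no event count is given for any survival endpoint. Nor do they say that P > 0.05 will be read as equal safety.

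**What to change.** Before the data are analysed:

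- **Section 5.4, tests.** Remove margins, complication rate and survival from the t-test/rank sum list.
- **Sections 5.4 and 6.3, margins.** Write one rule in both places, for example Fisher's exact test when any expected count is below 5, otherwise uncorrected chi-square. At 73 v 73 this means Fisher whenever positive margins total fewer than 10, because the expected count per group is half the total.
- **Reporting.** Give counts with an exact 95% CI per group and the risk difference with a Newcombe 95% CI. State that the named test alone decides significance and that the interval is descriptive; this settles a case such as 0 v 5. Report no ordinary odds ratio if a group has no positive margin.
- **Survival and recurrence.** Compare by Kaplan-Meier and log-rank with numbers at risk, beside the planned Cox model. If one group has no events, report the Kaplan-Meier results without a Cox hazard ratio.

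The cost is text in two sections and no new patients. Kaplan-Meier needs event and last-follow-up dates, which the Cox model needs anyway. The main downside is Fisher's conservatism (0.6% v 4.2% rejection at a common 3% rate), which makes a true difference in margins in either direction harder to declare.

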## **7. Informed consent**

Previous case information is used for this study and a waiver of informed consent is requested.

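### Follow-up renal function is compared with single-value tests and no rule for missing later values: precision is lost, each group's long-term mean can be biased, and the group difference can be biased if loss or early function differs between groups

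*Combined protocol and SAP*

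**What the plan says.** Section 2 lists the rate of change in GFR first among the efficacy measures. Section 3 evaluates "postoperative short-term, intermediate, and long-term renal function indexes" without dating any of the three horizons. For the between-group comparison, section 5.4 states that "T-test/rank sum test and one-way regression are used to compare the efficacy indexes such as negative/positive tumor margins, postoperative and follow-up renal function". Section 6.3 again gives the t-test for measurement data and the rank sum test for nonparametric variables.

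The other methods do not cover repeated GFR. Section 3 mentions multi-factor regression but does not assign it to follow-up renal function. Cox regression in 5.4 is for survival outcomes. The balancing in 5.2 concerns preoperative conditions only.

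The data are existing records: "This study used a retrospective research trial design", and "Previous case information is used for this study and a waiver of informed consent is requested". No section gives a follow-up schedule, an expected loss rate, a missing-data rule, a repeated-measures model or a sensitivity analysis.

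**The concern.** A t-test, rank sum test or one-factor regression on a late GFR value can include only patients who have that value. In records of past care, a late value exists only if the patient returned and was tested, and enough time had passed since surgery. Return could plausibly depend on early postoperative renal function, for example if a poor early result prompts renal follow-up. Balancing preoperative conditions, as in 5.2, does not correct for loss that depends on a postoperative value.

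Three things are at stake. Precision is lost even when loss is random, because an early value correlated with the missing late one goes unused. Each group's own long-term mean shifts when loss depends on early function; this matters because the main objective in section 2 concerns the enucleation group itself. The difference between the groups can also shift, and these are non-randomised surgical cohorts whose follow-up habits and early function may differ.

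**Working it through.** **Inputs from the documents.** The cohort is "73 patients who underwent zero-ischemic enucleation and 73 patients who underwent traditional partial nephrectomy from 2014 to 2022". On the level, "All hypothesis tests are two-sided, and differences are considered statistically significant at" P < 0.05 (section 6.3). The 73 comes from a two-proportion formula in section 3 whose inputs appear only as symbols ("Expected morbidity in the exposed group", and z-values that "are the quartiles under standard normal distribution"). With no p0, p1 or power stated it cannot be reproduced: 40% v 19% at 80% power and 30% v 9% at 90% power both give 73 (two-sided 0.05). It says nothing about GFR, so there is no planned renal-function power to check against.

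**Assumptions, not in the documents.** SD of percentage GFR change σ = 12 points at both times; early-late correlation ρ = 0.7; proportion with a late value π = 0.6 unless stated; probability of having a late value logistic in early function, with a slope per SD.

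**Step 1: precision under random loss, true difference 5 points.** Power is Φ(5/SE − 1.96).
- No loss: SE = 12√(2/73) = 1.99; power = Φ(0.56) = 71%.
- t-test on those with a late value: SE = 12√(2/(73 × 0.6)) = 2.56; power = Φ(−0.01), just under 50%.
- Likelihood analysis keeping early values: the variance factor 1/π = 1.667 becomes ρ² + (1 − ρ²)/π = 0.49 + 0.51/0.6 = 1.34; SE = 12√(2 × 1.34/73) = 2.30; power = Φ(0.21) = 58%.

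Simulation agrees: about 49% v 58%. The model recovers part of the lost power, not all of it.

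**Step 2: shift in one group's late mean.** If retained patients' mean early value is displaced by m SD, their late mean is displaced by σρm. Integrating the logistic retention curve over a normal early value gives:
- slope 1, 60% retained: m = 0.332, a shift of 12 × 0.7 × 0.332 = 2.8 points;
- slope 1, 80% retained: m = 0.173, a shift of 1.5 points;
- slope 0.5, 60% retained: m = 0.189, a shift of 1.6 points.

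The sign depends on whether worse or better early function brings patients back.

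**Step 3: group difference.** Bias is σρ times the difference in m between the groups.

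| Scenario | Bias, points | Type I error |
|---|---|---|
| Same mechanism, equal early function | about 0 | about 5% |
| Slopes 0.5 v 1, 60% retained | 8.4 × (0.332 − 0.189) = 1.2 | about 7% |
| One group only, slope 1, 80% retained | 8.4 × 0.173 = 1.5 | about 11% |
| One group only, slope 1, 60% retained (adverse) | 8.4 × 0.332 = 2.8 | about 20% |

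Type I errors are simulated; dividing bias by the SE gives 7.5%, 10% and 19% for the last three rows. In the adverse row, ρ from 0.5 to 0.8 moves bias from 2.0 to 3.2 points and type I error from about 12% to 26%.

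**Step 4: shared mechanism, true early and late difference of 5 points.** Retained patients' early means are displaced by 0.332 SD in one group and 0.269 in the other, so the estimate is 5 − 8.4 × (0.332 − 0.269) = 4.5. In simulation, power was 46% for the t-test and 60% for the likelihood analysis. This is attenuation, not a false positive.

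A likelihood analysis using the early value had bias near zero when loss depended only on that value.

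**The case against.** A reader might infer that any loss tied to early renal function biases the comparison of the two operations. It does not: with the same dependence and equal early function in both groups, the shifts cancel. A mechanism in which poor early function prompts follow-up would naturally act in both groups, and nothing in the documents shows that it acts differently.

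A reader might also take the 20% type I error as the expected size. It belongs to one adverse scenario. Neither the loss rate nor any between-group difference in dependence is documented, and milder assumptions give 7% to 11%, or no inflation.

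Nor do the documents show that an early value exists for every patient and is then discarded. Section 5.1 lists postoperative renal function changes as something to describe without speaking to completeness, and 5.4 does compare postoperative renal function. The early values are analysed; they simply do not inform the late comparison. Separate testing at each horizon is an inference from sections 3 and 5.4 together, though the natural one.

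Finally, some late values may be missing only for lack of time. The protocol is dated February 2023, surgery ran to 2022, and section 1 places nearly 100 zero-ischemia cases in the last three years. Such gaps need not depend on early function. And if patients were selected because follow-up was available, no model confined to them can repair that.

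All of this stands, and it limits the claim. It does not supply the missing rule or restore the lost precision.

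**Conclusion.** The concern holds in a limited form. The plan names only single-value methods for follow-up renal function and has no rule for missing later values, so late comparisons rest on whoever has a value. If any late values are missing, precision is lost: about 49% v 58% power under the stated assumptions. Each group's long-term mean is biased if loss depends on early function and early and late values are correlated. The group difference is biased only if the dependence or early function differs between groups; the illustrations run from about 0 to 2.8 points, the upper end being an adverse case. These figures rest on an assumed SD, correlation, loss rate and loss mechanism. No figure in the documents is contradicted. The change is worth making because the measure is the first-named efficacy outcome and a better method is cheap.

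**What to change.** In 5.4, make the main renal-function comparison one mixed model for repeated measures on all recorded postoperative GFR values. Fit group, time and group-by-time, with preoperative GFR as covariate; include every selected patient with at least one postoperative value; read the long-term group difference from the model.

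First define the short, intermediate and long-term windows, since the model needs them and section 3 does not date them. State whether availability of follow-up influenced selection of the 146 patients. Report by group the number with a value at each horizon, separating too little time since surgery from non-return. Keep the t-test as a sensitivity analysis and add one for loss not explained by recorded GFR.

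The cost is rewording, window definitions and modest extra analysis. The named software, SPSS 20.0, can fit the model, and no new data or visits are needed. The model assumes that loss is missing at random given the recorded values, and it cannot repair selection into the cohort on available follow-up.

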## **2. Research objectives**

Main objective: the efficacy (rate of change in renal function GFR, overall survival OS, tumor-free survival TFS, progression-free survival PFS, etc.) and safety (positive incision margin rate, intraoperative blood loss, postoperative complication rate, etc.) of unassisted zero-ischemia enucleation in the surgical treatment of patients with early stage (T1) renal cancer.

Secondary objectives: differences between unassisted zero ischemic enucleation of renal cancer and partial nephrectomy with clamping of the hilum in the surgical management of patients with renal cancer and the role of the modified ABC score in the assessment of renal cancer.

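### Later renal function has no time window and year of surgery is not a named balancing or adjustment variable, so the between-group comparison can mix operation with follow-up length and era

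*Combined protocol and SAP*

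**What the plan says.** Section 2 opens its list of efficacy measures with "rate of change in renal function GFR, overall survival OS" and makes "differences between unassisted zero ischemic enucleation of renal cancer and partial nephrectomy with clamping of the hilum" a secondary objective. Section 3 takes 73 patients per group, operated on from 2014 to 2022, and promises "postoperative short-term, intermediate, and long-term renal function indexes". It also states that "T-test, rank sum test, multi-factor regression, and cox regression are used to investigate the effects of each factor", without listing covariates.

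Section 5.1 puts the change in renal function after surgery among the perioperative data, next to margins and hospital stay. It puts follow-up renal function among the later data. Section 5.2 asks for "no statistical difference in the number of patients, gender age, tumor anatomy, renal function and other preoperative conditions between the two groups". Year of surgery is not named.

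Section 5.4 compares the groups by t-test or rank sum test, and "one-way regression are used to compare the efficacy indexes such as negative/positive tumor margins, postoperative and follow-up renal function, survival rate" appears in the same sentence. It then plans to examine "whether there are statistical differences in survival outcomes between the two groups by multifactorial cox regression". Section 6.3 assigns count data to chi-square or Fisher tests. Section 1 counts more than 500 enucleations over ten years, but puts nearly 100 zero-ischaemia cases in the last three.

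**The concern.** In a retrospective series closed at one date, year of surgery fixes the longest follow-up a patient can have. If zero-ischaemia patients were operated on later than controls, two things follow.

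- **Reading time.** A long-term GFR without a window will tend to be an earlier reading in the zero-ischaemia group and a later one in controls. If GFR declines with time in everyone, a difference in favour of zero ischaemia appears with no surgical effect.
- **Era.** Selection, technique and care may change between 2014 and 2022. Cox regression deals with unequal follow-up, but an era effect on outcome enters the hazard ratio unless year is in the model. Its direction cannot be known from the documents.

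A smaller point concerns the survival rate, which section 5.4 lists under the t-test and rank sum test. Applied to a dead/alive variable, these ignore time at risk, and they can give a result that conflicts with the planned Cox regression.

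**Working it through.** The plan gives no figure to reproduce here, and no surgery dates by group. What follows is an illustration.

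**Inputs from the documents:** 73 per group and surgery 2014–2022 (section 3); document date 10 February 2023; two-sided 5% level (section 6.3); nearly 100 zero-ischaemia cases in three years (section 1).

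**Assumptions:** the cut-off is the document date. Follow-up in years is uniform on (0.11, 3.0) for recent zero-ischaemia cases. For controls it is uniform on (0.11, 3.0) if contemporaneous, (0.11, 9.11) if spread over 2014–2022, and (3.11, 9.11) if all from 2014–2019. Long-term GFR is the last reading at 12 months or later. Both groups decline by 1 unit per year, SD 15, with no effect of operation.

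**Step 1, readings and mean reading time.**
- Zero-ischaemia, all recent: n = 73 × 2/2.89 = 50.5; mean (1 + 3)/2 = 2.0 years.
- Controls, uniform: n = 73 × 8.11/9 = 65.8; mean (1 + 9.11)/2 = 5.06 years.
- Controls, 2014–2019: n = 73; mean (3.11 + 9.11)/2 = 6.11 years.

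**Step 2, false-positive rate.** With d = slope × difference in mean time, SE = 15 × √(1/n₁ + 1/n₀) and z = d/SE, the rate is Φ(z − 1.96) + Φ(−z − 1.96).

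| Controls | d | SE | z | Rate | Rate, follow-up stopped at 3 years |
|---|---|---|---|---|---|
| Contemporaneous | 0 | 2.98 | 0 | 5% | 5% |
| Uniform 2014–2022 | 3.06 | 2.81 | 1.09 | 19% | 5.8% |
| All 2014–2019 | 4.11 | 2.75 | 1.50 | 32% | 6.5% |

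Stopping at three years brings the control mean to 2.75 (uniform) or 3.0 (2014–2019), so d is 0.75 or 1.0.

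**Step 3, share of recent zero-ischaemia cases.** With uniform controls and no stop, if the older zero-ischaemia cases are uniform on (3.0, 9.11), the mean reading time rises to 3.3 years with 75% recent and 4.4 with 50%. The rate is then 10% and 6%. With all recent, slopes of 0.5 and 1.5 give 8.5% and 37%.

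**Step 4, effect of a window.** Within a common window of ±3 months, reading times differ by at most 0.5 years. At 0.5–1.5 units per year the false difference is at most 0.25–0.75 units.

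**Step 5, era in Cox.** Take uniform controls, equal operations and no year in the model. The limiting hazard ratio is the root of the large-sample partial-likelihood score. If surgery before the last three years carried 1.5 times the hazard, it is 0.72 (all recent), 0.91 (75%) or 0.97 (50%). If it carried 0.67 times the hazard, it is 1.34, 1.12 or 1.04.

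**Step 6, crude survival.** Take equal hazards of 1, 2 or 3% per year, all zero-ischaemia cases recent, and uniform controls. Exact binomial enumeration gives false-positive rates of 15, 31 and 43% for a t-test on the 0/1 outcome, and 4, 17 and 31% for Fisher. With a three-year stop they are 4, 8 and 11%, and 0.4, 2 and 5%.

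**The case against.** The main objection is that the dates are unknown. The three-year statement describes the team's caseload, not the study sample, and section 3 gives 2014–2022 for the included patients. With contemporaneous controls, or with follow-up that stops at three years, the GFR bias is close to nil. This stands, and it is why the size is given as a range.

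Several stronger readings are tempting, and the documents do not support them.

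- **That no planned analysis could deal with timing or era.** Section 3 plans multi-factor regression as well as Cox, and the last item in the section 5.2 balancing list is open-ended. Year or reading time is neither included nor excluded. What can be said is that no guard is stated.
- **That all renal function is exposed.** Section 5.1 ties the early change to the perioperative period, which depends little on length of follow-up. The gap concerns intermediate, long-term and follow-up readings.
- **That the plan holds rival definitions of one GFR outcome.** Section 5.3, where "the percentage decrease of postoperative renal function compared with preoperative, perioperative complication rate and postoperative survival rate are used as outcome variables", is an analysis within the zero-ischaemia group by tumour score. The rate of change in section 2 could also mean change per unit time, which under a common linear decline would give no false difference. The text does not say which is meant.
- **That a time-to-event analysis is missing.** Cox regression is planned for survival outcomes, and the one-way regression in section 5.4 may be univariable Cox. The listing of survival rate is a matter of wording.

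Figure 2 is not shown, so it cannot be checked for time points.

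**Conclusion.** The concern holds as a gap in specification, worth correcting before the comparison is run. In the readable text, later renal function has no window, year of surgery is not named in section 5.2, and covariates are not listed. Following sections 5.2 and 5.4 as written can therefore bias the comparison of operations.

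Later surgery in the zero-ischaemia group is plausible, not established. In the illustration the GFR false-positive rate runs from nominal to about one in three, and control dates alone move it across that range. The Cox and crude-survival figures depend in addition on assumed hazards and era effects, and were computed only with uniform control dates. Since section 1 reports no local recurrence in over 500 enucleations, inflation for that endpoint is probably small.

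The effect is confined to the between-group comparison, a secondary objective. Confidence is medium.

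**What to change.** 1. **Section 5.2:** name year of surgery as a balancing variable, or adjust for it in the between-group regressions. Where surgery years barely overlap, restrict the comparison to the overlapping years and present the rest as descriptive.
2. **Sections 3 and 5.4:** define intermediate and long-term renal function as postoperative windows, identical in both groups and chosen from what the records hold. Compare GFR change from the preoperative value within each window.
3. **Section 5.4:** take survival rate out of the t-test/rank-sum sentence. Compare OS, TFS, PFS and recurrence only by time-to-event methods, from date of surgery to event or last contact.
4. **Reporting:** give surgery dates and follow-up by group, and limit comparative conclusions to the follow-up that both groups cover.

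**Cost.** Mostly wording, but balancing on year loses precision. With uniform control dates, 73 × 2.89/9 = 23.4 controls are recent and 49.6 older. Weighting them to the zero-ischaemia dates leaves about 23, 40 or 64 effective controls (100, 75 or 50% recent). The interval ratio √[(1/73 + 1/ESS)/(2/73)] is 1.43, 1.19 or 1.04, so intervals are 43, 19 or 4% wider.

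Events are few. At 1–3% per year, all recent and with no stop, about 4 to 13 are expected in total, so the Cox model can carry few covariates.

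Readings outside the windows are lost. With all zero-ischaemia cases recent, 51, 25 and 0 of them could have 12, 24 and 36 months of follow-up, against 66, 58 and 50 uniform controls. A long-term comparison may not be possible, which is better known beforehand.
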